Version B	10 FEB 2017	Changed Painful Peripheral Diabetic Neuropathy to Diabetic Peripheral Neuropathy to allow for a broad symptomatology to be included. Added information to how many times VPT test will be conducted to obtain the average value at each time point. Added additional primary endpoint to capture changes in both large and small nerve fiber responses. Updated response assessment from VPT change to change in 1-point decrease in NPRS over the last 24 hours. Added additional instruction and a visual for collecting the foot measurement, updated introduction and background section, and added additional medications to "allowed medications" section. Removed EQ-5D questionnaire and replaced with Neuro-QoL questionnaires.
Version C	22 FEB 2017	Change testing of plantar aspect to dorsal aspect for QST heat and cold testing. Updated Exclusion #3 added a timeframe of within 6 months of the Screening Visit and an upper limit of 1.4 for the ABI.
Version D	27 MAR 2017	Removed Summary of Diabetes Self Care Activities Questionnaire (SDSCA) to reduce patient fatigue with answering questionnaires. Switched NeuroQoL questionnaire with a single neuropathy-and foot ulcer-specific quality of life instrument.
Version E	19MAY2017	Updated locations for biopsies to be taken as well as the central lab used in analyzing the samples.
Version F	12JUN2017	Increase the number of sites from 2 to 4. Update Inclusion/Exclusion criteria to allow for a broader population to be enrolled. Allow all patients to voluntarily consent to biopsies.

Study Title Protocol Number Name of Study Device Phase of Development Objective	AMulti-Center,Sham-Controlled,Double-BlindRandomized Withdrawal Study of Pulsed ElectromagneticField (PEMF) Therapy to Evaluate Vibration PerceptionThreshold and Thermal Sensory in Subjects with DiabeticPeripheral Neuropathy in the Lower ExtremityRBI.2017.001PROVANT® Therapy SystemProof of ConceptTo demonstrate the effectiveness of PEMF treatment compared
	to sham treatment in changing Vibration Perception Threshold (VPT) and Thermal Sensory (QST) in patients with diabetic peripheral neuropathy (DPN) when treatment is administered twice daily through 120-day period.
Number of Subjects	Up to 40 subjects randomized 1:1.
Study Design	This is a multi-center, sham-controlled, double-blind, enriched enrollment, randomized withdrawal clinical trial conducted on subjects with bilateral symmetrical diabetic peripheral neuropathy. Eligible subjects will include those between 22 and 80 years of age with Type 1 or Type 2 diabetes having persistent pain, numbness, tingling, or burning in both feet despite treatment. Eligible subjects will receive two active treatment devices (one for each foot, to allow simultaneous treatment) and treat at home, twice daily for 60 days after which they will return to the clinic at Day 61 for a response assessment. Subjects that are determined to be responders at Day 61 (subjects that achieve a 1-point decrease in the average pain score over the last 24 hours using the Numeric Pain Rating Scale (NPRS)) will be randomized 1:1 to either active treatment or inactive sham devices and will continue treating through Day 120. Subjects that are determined to be non-responders at Day 61 will continue treating with the active devices given at enrollment and will return to the clinic at Day 75 and Day 91 for a response assessment. If a subject is determined to be a responder at Day 75, they will be randomized 1:1 to receive either active treatment or inactive sham and will continue treating through Day 120. If a subject is determined to be a responder at Day 91, they will be randomized 1:1 to receive either active treatment or inactive sham and will continue treating through Day 120. If a subject is determined to be a responder at Day 91, they will be randomized 1:1 to receive either active treatment or sham and will continue to treat through Day 120. If a subject continues to be a non-responder at Day 91 they will be terminated from the study.

Endpoints	For this proof of concept study, the primary endpoints will be changes in Vibration Perception Threshold and Quantitative Sensory Testing between baseline and end of treatment. Secondary endpoints will be changes in nerve conduction velocity (NCV) of the sural nerve and amplitude from baseline to end of treatment, changes in Skin Perfusion Pressure (SPP) from baseline to end of treatment, change in Pain Intensity using the 11-point Numeric Pain Rating Scale (NPRS) from baseline to end of treatment, change from baseline in Brief Pain Inventory (BPI) and Brief Fatigue Inventory (BFI), change from baseline in Patient Global Impression of Change (PGIC), change from baseline in Hospital Anxiety and Depression Scale (HADS), and changes from baseline in neuropathy and foot ulcer specific quality of life instrument (NeuroQoL).
	Safety will be assessed through review of Adverse Event (AE) reports and concomitant treatments and medications. All concomitant drug or non-drug treatments used during the study will be recorded. Safety outcomes will be assessed at the interim visits and the end of study visit.
Study Procedures	Following informed consent and assessment of eligibility, subjects will complete Section A-History of the Michigan Neuropathy Screening Instrument (MNSI) with Section B- Physical Assessment completed by the site. A measurement of the depth of the right foot will be measured from the most inferior aspect of the medial malleolus to the plantar aspect of the foot when residing on the treatment pad. The depth should not be more than 8cm for eligibility. A finger stick will be performed on the subject to obtain a baseline HbA1c value (A1C Now [®] test kit) and subjects will complete a Urine Drug Screen in office. Subjects will undergo the Ankle-Brachial Index (ABI), Venous Insufficiency Assessment, and Pain Phase evaluation (at least 10 subjects in each of the 2, 3, and 4 pain phases will be enrolled). For subjects of child bearing potential a urine pregnancy test will be obtained.
	At the Enrollment Visit (can be combined with Screening), subjects will have a finger stick performed to collect a baseline glucose value. If the Screening Visit and Enrollment Visit are not combined, eligibility will be re-assessed to confirm no changes, concomitant medications and assessments of Adverse Events will be obtained. Subjects will provide their baseline pain score over the last 24 hours using the Numeric Pain Rating Scale (NPRS) and will also complete baseline health economic questions, questionnaires including the Brief Pain Inventory (BPI), Brief Fatigue Inventory (BFI), Hospital Anxiety and Depression Scale (HADS), and the NeuroOoL Ouestionnaire.

Vibration Perception Threshold (VPT), Quantitative Sensory Test (QST) and Nerve Conduction Velocity (NCV) will be performed. Skin Perfusion Pressure (SPP) will be performed to obtain a baseline value of the plantar and dorsal aspect of the right foot. Eligible subjects will receive 2 active treatment devices (1 device for each foot). Subjects will be instructed in the use of the devices and will self-treat both feet twice daily (morning and evening; $8am \pm 2$ hours and $8pm \pm 2$ hours) for 60 days in the home environment. Each treatment will be 30 minutes in duration, treating both feet simultaneously. Subjects will be provided with a study diary for capturing their daily pain scores based on a 11-point numerical pain rating scale (NPRS) and weekly Patient Global Impression of Change Score (PGIC). Subjects will document pain scores each day after the morning treatment as instructed by the site at the Enrollment Visit. Every week the PGIC will be collected in the diary and the subject will document their overall status since the beginning of treatment. Subjects will either provide consent or not for biopsies to be obtained. Subjects that consent to the biopsies will have two 3mm punch skin biopsies obtained, one biopsy at the distal leg (10cm above the lateral malleolus) and one biopsy at the distal thigh (10cm above the superior margin of patella). Biopsies will be taken from the right leg to represent small nerve fiber innervation emanating from the deep peroneal nerve. At least two subjects in each pain phase category (2, 3, and 4 Pain Phase) will be obtained.

The site will contact the subject via telephone on Day 3 to assess subject adherence to treatment, completion of the diary, and any safety concerns and/or changes in concomitant treatments/medications.

At Days 15 and 45, subjects will return to the clinic to have VPT and QST conducted and to have treatment satisfaction assessed. Subjects will also bring in the study devices and diary to assess treatment and diary compliance. A new study diary will be dispensed for the next two weeks.

At Days 30 and 61, subjects will return to the clinic to complete the BPI, BFI and HADS questionnaires and to have treatment satisfaction assessed. VPT and QST will be conducted along with a finger stick to collect the subject's blood glucose level. Subjects will also bring in their study devices and diary to assess treatment and diary compliance. A new study diary will be dispensed for the next two weeks. At Day 61, SPP will be conducted and subjects will be assessed for a response. If a subject is determined to be a responder (decrease in average pain score over the last 24 hours using the NPRS of at least 1 point)

they will return the active devices and be randomized 1:1 to receive active treatment or inactive sham devices and be instructed to treat for an additional 60 days (through Day 120). If the subject is determined to be a non-responder, they will continue treating with the active devices for an additional 15 or 30 days and will be assessed at Day 75 and Day 91 for response. At Day 75, subjects will return to the clinic to have treatment satisfaction assessed, and have the VPT and QST conducted. All subjects will bring in their devices and diary to assess treatment and diary compliance. A new study diary will be dispensed for the next two weeks. For those subjects determined to be nonresponders at Day 61, they will be assessed for response. If they become a responder by Day 75 they will return their active devices and be randomized 1:1 to receive active treatment or inactive sham devices, and instructed to treat through Day 120. If the subject is still considered a non-responder, they will continue treating through Day 90 with the active devices given at Enrollment. At Day 91, subjects will return to the clinic to complete the BPI, BFI and HADS questionnaires and to have treatment satisfaction assessed. The VPT and QST will be conducted along with a finger stick to collect the subject's blood glucose level. Subjects will also bring in the study devices and diary to assess treatment and diary compliance. A new study diary will be dispensed for the next two weeks. At Day 91, non-responders will be assessed for a response. If a subject is determined to be a responder at Day 91 (decrease in average pain score using the NPRS of at least 1 point) they will return the active devices and be randomized 1:1 to receive active treatment or inactive-sham devices and instructed to treat for an additional 30 days (through day 120). If the subject is determined to be a non-responder, they will be terminated from the study at the end of the Day 91 visit. At Day 105, all subjects will have VPT and QST completed and have treatment satisfaction assessed. Diaries will be collected and a new diary dispensed. Subjects will also bring in the study devices and diary to assess treatment and diary compliance. At Day 121, end of study visit, subjects will have their weight, ABI, NCV, SPP, and Venous Insufficiency assessed. Subjects will also receive a finger stick to obtain blood for the HbA1c and blood glucose values. The subject will complete the BPI, BFI, HADS, and NeuroQoL questionnaires and have treatment satisfaction assessed. The subject will return their study devices and diary, and the VPT and QST will be completed. Subject's that consented to having the biopsy, will have a 3mm punch skin biopsy obtained from the distal leg and distal thigh on the right

	leg. The biopsy will be obtained to represent small nerve fiber innervation emanating from the deep peroneal nerve.
	Assessment of adverse events and concomitant medications will occur at each visit.
Study Device	The study device is the PROVANT [®] Therapy System (PEMF). The active devices will deliver Pulsed Electromagnetic Field (PEMF) energy therapy. The active treatment and inactive sham devices will be identical in appearance and all other physical characteristics in order to maintain the blinding of the treatment. Each device will be identified with a unique kit number.
Study Sample	The anticipated enrollment in this study is up to 40 subjects. The study will be conducted at up to 4 sites.
Primary and Secondary Outcome Measures	Several efficacy outcome measures will be assessed in order to allow for characterization of the response to PEMF therapy.
	Efficacy Assessments
	All efficacy assessments will be conducted at the Enrollment Visit (Baseline; Day 0) and at the end of study visit (Day 121).
	Vibration Perception Threshold (VPT): For large nerve fiber assessment. VPT is a non-invasive test used in quantifying sensation/sensitivity to vibration in evaluating sensory dysfunction associated with diabetic neuropathy. The hand-held vibratory stimulator will be placed against the midpoint of the plantar aspect and big toe of the right foot, the tester will initiate the automated test that will last between 5-10 minutes. Three tests will run at each location and the average of the 3 will be populated by the system. The VPT will be collected using the VSA-3000 Vibratory Sensory Analyzer at the midpoint on the plantar aspect and on the big toe of the right foot. VPT will be collected at the Enrollment Visit to obtain a baseline value and on Days 15, 30, 45, 61, 75, 91, 105 and 121.
	Quantitative Sensory Testing (QST): For small nerve fiber assessment. QST is a noninvasive test used in peripheral nervous system disorders for thermal sensory testing. Contact thermal stimulation will be delivered using the NerveCheck Master through a contact thermode. A cold test of 15° C - 25° C, heat test of 40° C - 46° C will be administered. When activated the patient will notify the staff performing the test when they begin to feel the cold and warm test. The heat and cold thermal stimulation will be applied over the dorsal aspect of the right foot. QST will be performed at the Enrollment Visit to obtain a baseline value and on Days 15, 30, 45, 61, 75, 91, 105 and 121.

Nerve Conduction Velocity (NCV): For large myelinated nerve fiber assessments. Using the NC-stat[®] DPNCheck[®], the subject will assume a comfortable position so that their right leg is visible (that the subject's outer ankle bone and Achilles tendon are visible). The patient preparation pad is then used to thoroughly clean the subject's outer lower leg and ankle bone area to remove any residue. The subject's outer ankle bone is then identified to align the anode and cathode just behind with the cathode just adjacent to the middle of the ankle bone. The device is aligned on the calf pressing firmly down on the foam to ensure contact. The sural nerve conduction velocity and amplitude will be recorded at the Enrollment Visit and end of study visit (Day 121). Skin Perfusion Pressures (SPP): Vasamed Sensilase PAD-IQ measures pressure (in mm Hg) of microcirculation using a laser Doppler sensor. Patient lies down in supine position and remains silent and still. The Laser Sensor Assembly (LSA) is inserted into the LSA Placement Guide and the optical sensor window is oriented toward the skin. For those subjects who will have biopsies performed, SPP will be obtained prior to the skin biopsies. A cuff is positioned so that the LSA is centered on the bladder both horizontally and vertically. The pressure of the cuff is then automatically increased to a pressure necessary to occlude blood flow and then released at a controlled rate and a measurement of the pressure in the angiosome is made. SPP (mmHg) at reactive hyperemia is recorded. A second measure of SPP will be obtained on the plantar aspect of the right foot directly below the location where the SPP was performed on the dorsal aspect of the right foot. SPP will be conducted at the Enrollment Visit, Day 61, and end of study visit (Day 121). Pain Intensity (PI): a validated 11-point Numeric Pain Rating Scale (NPRS) with scores (0-10) collected as patient-reported outcomes on a paper diary and at the Enrollment visit to obtain a baseline value and on Days 61, 75, and 91 to determine response. On the patient diary, PI will be assessed after each morning (8am ± 2 hours) treatment. Subjects will report their average pain score over the last 24 hours. Diaries will be distributed and collected from the subjects every 2 weeks to ensure compliance. Brief Pain Inventory (BPI): is a 32-question long form questionnaire that assesses the severity of pain and its impact on specific daily functions. Cronbach's alpha reliability ranges from 0.77-0.91. The BPI long form will be administered at the Enrollment Visit, Day 30, 61, 91, and end of study visit (Day 121). **Brief Fatigue Inventory (BFI):** is a 4-question assessment that assesses the level of fatigue and the impact of the fatigue on daily

	function over the last 24 hours. A global fatigue score is collected by averaging all items on the BFI. Cronbach's alpha reliability ranges from 0.82-0.97. BFI is patient reported and collected at the Enrollment Visit, Days 30, 61, 91, and end of study visit (Day 121).
	Patient Global Impression of Change (PGIC) : a 7-point validated categorical scale of overall change in status since initiation of treatment with the study device. PGIC allows subjects to integrate, into one overall evaluation, the different aspects of their response to treatment, including pain reduction, improvement in functioning and side effects. PGIC will be collected every 7 days in the paper diary, immediately following the morning treatment. PGIC serves to anchor within-subject changes in pain over the course of treatment.
	Hospital Anxiety and Depression Scale (HADS): is a patient reported assessment that detects stats of depression and anxiety. The subscales within the assessment assess the severity of the emotional disorder connected to having diabetic peripheral neuropathy. Subjects will complete the assessment at the Enrollment Visit, Days 30, 61, 91, and end of study visit (Day 121).
	NeuroQoL: is a validated assessment that measures the effects of diabetic peripheral neuropathy and its complications on an individual's quality of life. The questionnaire will be completed by the subject at the Enrollment Visit and end of study visit (Day 121).
	Experimental Outcome Assessment
	Skin Biopsy: To assess c-fiber nerve density. Subjects that provide consent to having biopsies taken will have two 3mm punch skin biopsies obtained, one biopsy at the distal leg (10cm above the lateral malleolus) and one biopsy at the distal thigh (10cm above the superior margin of patella) on the right leg at the Enrollment Visit. At least 2 subjects in each pain phase category (2, 3, and 4 Pain Phase) will have a biopsy obtained. The biopsy will be shipped overnight to the central lab for processing. At the Day 121 Visit, a second set of biopsies will be obtained to the right of each prior biopsy on the distal leg and distal thigh of the right leg. The samples will be shipped overnight to the central lab for processing. The lab will assess the samples for nerve fiber density and compare to baseline.
Statistical Considerations	This bi-phasic design includes 2 sequential periods: the Induction Phase and Randomized Withdraw Phase . All safety analyses will

be performed on the safety analysis set, defined as all subjects who were enrolled into the study and issued study devices during the Induction Phase and followed through the Randomized Withdraw Phase . Once the subject is determined to be eligible, the subject will be issued active treatment devices and the subject will be formally enrolled into the study and become part of the Safety Analysis Set .
All recorded data will be listed by subject and time point. Descriptive statistics will be tabulated for all randomized subjects for the change from baseline to study day 120 (Completers Analysis Set), and separately for the change from baseline to the last recorded set of evaluations (End of Study Evaluation Set). This latter set should include all subjects who were randomized and complete at least one set of evaluations after randomization.
Treatment-emergent adverse events will be summarized by type, frequency, severity, and relationship to the study device. Adverse events will be provided in a listing.

Ι.	INTRODUCTION AND BACKGROUND	17
II.	STUDY OBJECTIVES	23
III.	STUDY DESIGN	24
Α.	Study Design	24
В.	EFFICACY ENDPOINTS	26
C.	SAFETY EVALUATION	26
D.	ELIGIBILITY CRITERIA	26
1.	Inclusion Criteria	
2.	Exclusion Criteria	27
Ε.	RECRUITMENT	29
F.	RANDOMIZATION	29
G.	DEVICE DESCRIPTION	29
1.	Control Unit	29
2.	Disposable Applicator Covers	
З.	Treatment Applicator	
Н.	LOGISTICS AND DEVICE ACCOUNTABILITY	
١.	LABELING	31
J.	Preparation and Administration	32
К.	Blinding	
L.	Study Assessments	
1.	Primary Efficacy Assessments	
2.	Secondary Efficacy Assessment	
З.	Exploratory Efficacy Assessment	35
4.	Additional Study Assessments	35
5.	Safety Assessments	
IV.	STUDY PROCEDURES	
Α.	VISIT 1 – SCREENING VISIT (DAY -14 TO 0)	
В.	VISIT 2 – ENROLLMENT VISIT (DAY 0)	
C.	Day 3 Phone Call (Day 3 +2 Days)	
D.	Day 15 Interim Visit (Day 15 + 3 Days)	
Ε.	Day 30 Interim Visit (Day 30 + 3 Days)	
F.	Day 45 Interim Visit (Day 45 + 3 Days)	40
G.	Day 61 Visit (Day 61 +3 Days)	40
Н.	Day 75 Interim Visit (Day 75 + 3 Days)	41
١.	Day 91 Visit (Day 91 +3 Days)	41
J.	Day 105 Interim Visit (Day 105 + 3 Days)	42
К.	Day 121 Visit (Day 121 + 3 Days)	42
L.	TREATMENT ADHERENCE/STUDY COMPLIANCE	43
M.	PROTOCOL ADHERENCE	43
N.	CONCOMITANT MEDICATIONS	43

1.	Allowed Medications
2.	Prohibited Medications/Treatments
v .	WITHDRAWAL PROCEDURES45
VI.	STATISTICAL CONSIDERATIONS
Α.	INDUCTION PHASE / BASELINE EVALUATIONS
В.	Randomized Withdraw Phase
C.	SUMMARIZATION OF RESULTS

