The purpose of the current study is to further elucidate the underlying mechanisms of increased sensation and pain relief observed in patients receiving treatment with the PROVANT[®] Therapy System. In vitro studies have provided evidence that PEMF therapy improves nerve growth and may improve nerve function through up-regulation of genes involved in neurogenesis. [Data on File] In addition, genes related to angiogenesis have also been shown to be up-regulated. Through evaluation of vibration perception threshold, nerve conduction velocity, quantitative sensory testing, vascular changes (skin perfusion pressure), blood glucose (hemoglobin A1c), and quality

of life questionnaires, this study will evaluate if PEMF treatment in vibration perception and skin perfusion is enhanced in subjects that receive treatment with Provant compared to a group of subjects that receive treatment with a sham device.

II. STUDY OBJECTIVES

This study is designed to evaluate the effectiveness of the PROVANT[®] Therapy System (PEMF) in changing Vibration Perception Threshold (VPT) and Thermal Sensory Perception using Quantitative Sensory Testing (QST) in patients with bilateral symmetrical diabetic peripheral neuropathy (DPN) when treatment is administered twice daily through a 120-day period.

III. STUDY DESIGN

A. Study Design

The study is a multi-center, sham-controlled, double-blind, enriched enrollment randomized withdrawal study of the safety and efficacy of multi-dose PEMF therapy on subjects with bilateral symmetrical DPN. A graphic presentation of the study design is shown in Figure 1.

25

B. Efficacy Endpoints

This study will evaluate the changes in vibration perception threshold, thermal sensory perception, nerve conduction velocity, skin perfusion pressure, pain intensity, brief pain inventory, brief fatigue inventory, PGIC, hospital anxiety and depression scale, and neuropathy specific quality of life.

C. Safety Evaluation

All observed and reported adverse effects will be recorded by the research staff. Start dates, end dates, frequency, severity of the event, any treatment required to treat the event, and the investigator's judgment on causality and relationship to the study device will be assessed for each AE. Any AE occurring after the signing of the informed consent form will be recorded. Only those AEs occurring after initiation of the first treatment with the study device will be considered treatment-emergent AEs.

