At the start of this study, all subjects will receive active devices. At Day 61, Day 75, or Day 91, if the subject becomes a responder based on a 1-point decrease in the average pain score using the Numeric Pain Rating Scale, the subject will be randomized 1:1 (active: sham). The sham devices will be PEMF devices that are de-activated such that no radiofrequency energy is generated or delivered when the device is started. All other functions, including the start sequence, display lights, audible start-beep and fan operation of the sham devices are identical to that of the active PEMF devices. Sham devices are indistinguishable from the active PEMF devices being used in the study. The subjects, research personnel at the investigative site, and sponsor will be fully blinded to the randomization assignment and unable to differentiate active and sham devices.

L. Study Assessments

All efficacy outcome measures will be assessed in order to allow for characterization of the response to PEMF therapy. All efficacy assessments will be conducted at the Enrollment Visit (Baseline; Day 0) and at the end of study visit (Day 121).

1. Primary Efficacy Assessments

Vibratory Perception Threshold (VPT): For large nerve fiber assessment. VPT is a non-invasive test used in quantifying sensation/sensitivity to vibration in evaluating sensory dysfunction associated with diabetic neuropathy. The hand-held vibratory stimulator will be placed against the midpoint of the plantar aspect and big toe of the right foot; the tester will initiate the automated test that will last between 5-10 minutes. Three tests will run at each location and the average of the 3 will be populated by the system. The VPT will be collected using the VSA-3000 Vibratory Sensory Analyzer at the midpoint on the plantar aspect and on the big toe of the right foot. VPT will be collected at the Enrollment Visit to obtain a baseline value and on Days 15, 30, 45, 61, 75, 91, 105 and 121.

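### The Synopsis objective is PEMF versus sham over 120 days, but the randomised comparison can only address continuing active PEMF versus switching to sham for 30 to 60 days in pain responders

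*Combined protocol and SAP*

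**What the plan says.** **Objective.** The Synopsis sets out to demonstrate effectiveness of PEMF relative "to sham treatment in changing Vibration Perception Threshold (VPT) and Thermal Sensory (QST) in patients with diabetic peripheral neuropathy (DPN) when treatment is administered", and attaches a duration: "when treatment is administered twice daily through 120-day period". The closing sentence of Section I says that vibration perception and skin perfusion will be compared between subjects treated with the device and a group treated with a sham device; it gives no duration. Section II claims effectiveness on VPT and QST in "bilateral symmetrical diabetic peripheral neuropathy (DPN) when treatment is administered twice daily through a 120-day period", without naming sham.

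**Design.** Section III.K states: "At the start of this study, all subjects will receive active devices". The Synopsis (Study Design) has subjects treat "twice daily for 60 days after which they will return to the clinic at Day 61 for a response assessment". Those with a 1-point decrease in 24-hour average NPRS at Day 61, 75 or 91 are randomised 1:1 to active or sham and treat through Day 120. Day 91 non-responders leave the study unrandomised (Section VI.B). The Synopsis (Study Procedures) gives the post-randomisation period as 60 days for Day 61 responders and 30 days for Day 91 responders.

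**Analysis.** The primary endpoints are changes in VPT and QST from baseline to end of treatment (Synopsis, Endpoints). Section VI.C defines baseline as the last value before the first active treatment and tabulates randomised subjects only. It plans differences between groups with 95% confidence intervals, and p-values below 0.05 are to be discussed as statistically significant. Section VI.E says that no formal test is planned and that the 40 subjects are a sample of convenience.

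**The concern.** The stated objective and the randomised comparison are different quantities. The objective concerns 120 days of PEMF against sham in diabetic peripheral neuropathy. The only sham-controlled comparison starts after at least 60 days of active treatment, is restricted to subjects selected on pain, and runs for the last half or less of the treatment period.

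What is at stake is how the result may be read. If an active-sham difference on VPT or QST at Day 121 is set against the objective as written, it can be taken as the effect of 120 days of PEMF. It would in fact show an effect of continuing rather than stopping. If there is no difference, the objective invites the conclusion that PEMF does not change VPT or QST. That does not follow when both arms have had 60 to 90 days of active treatment and nothing rules out carry-over.

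**Working it through.** **Step 1. Reproduce the plan's own figures.** Longest sham exposure = last treatment day − randomisation day + 1.

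- Day 61: 120 − 61 + 1 = 60 days, as the Synopsis states.
- Day 91: 120 − 91 + 1 = 30 days, as the Synopsis states.
- Day 75: 120 − 75 + 1 = 46 days (not stated; same formula).

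**Step 2. Active exposure in the sham arm.** Active lead-in = randomisation day − 1.

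| Randomised at | Active lead-in (days) | Longest sham (days) | Share of 120 days on active | Share on sham |
|---|---|---|---|---|
| Day 61 | 60 | 60 | 60/120 = 50% | 50% |
| Day 75 | 74 | 46 | 74/120 = 62% | 38% |
| Day 91 | 90 | 30 | 90/120 = 75% | 25% |

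Visit windows (+3 days) change little. Randomisation at the late limit gives 57, 43 or 27 days of sham. If a Day 61 responder kept treating until an end visit on Day 124, the maximum would be 123 − 61 + 1 = 63 days. No subject can have 120 days of sham.

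**Step 3. What the comparison estimates.** Let *L* be the mean change during the active lead-in, *A* the mean later change on active and *S* the mean later change on sham.

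- Change from baseline, active arm: *L* + *A*
- Change from baseline, sham arm: *L* + *S*
- Difference between arms: (*L* + *A*) − (*L* + *S*) = *A* − *S*

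Randomisation comes after the lead-in, so *L* has the same expectation in both arms and cancels. The effect named in the objective would be (*L* + *A*) − *P*, where *P* is the change over 120 days in subjects given sham from the start. *P* is not observed in any subject. *L* is observed, but without a control.

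**Step 4. How far *A* − *S* can lie from a 120-day effect *E*.** The documents give no rate of gain or loss, so these are assumptions, shown only for their range. Change without PEMF is taken as zero.

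- Gain accrues linearly and is fully retained on sham: *A* − *S* is 50%, 38% or 25% of *E* for randomisation at Day 61, 75 or 91 (the sham shares in Step 2).
- Gain accrues linearly and is wholly lost on sham: *S* = −*L*, so *A* − *S* = *A* + *L* = 100% of *E*.
- Gain is complete before randomisation and fully retained: *A* = *S* = 0, so *A* − *S* = 0.

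The same true effect can therefore appear as anything from none to all of itself.

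**Step 5. Population.** The objective names patients with diabetic peripheral neuropathy. Only NPRS responders enter the randomised tables, and they are selected on pain rather than on VPT or QST.

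**The case against.** The strongest reply is that the design is disclosed. The title calls the trial a randomised withdrawal study, Section III.A adds enriched enrolment, and Sections III.G.1, III.K and VI.B describe the active lead-in and responder-only randomisation. The 120-day period can be read as total time on study devices, and nowhere does the protocol claim 120 days of sham. This is an unpowered proof-of-concept study with no success rule. All of that is true, and it makes the matter one of interpretation. It does not close the gap: the Synopsis still ties the 120 days to a comparison with sham, no objective is worded as continuation versus withdrawal, and Section VI.C plans between-group estimates and discussion of statistical significance that will be read against that objective.

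Four stronger readings are tempting, and the documents do not support them.

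- *Section II makes the same sham claim.* It does not mention sham. Only the Synopsis joins sham with 120 days.
- *The protocol's mechanism predicts that gains persist after stopping.* Section I reports in vitro evidence that "PEMF therapy improves nerve growth and may improve nerve function through up-regulation of genes involved in neurogenesis", but it also proposes endogenous opioids and reduced inflammation as routes to pain relief. It says nothing about durability. Carry-over is possible, not predicted.
- *The share of the effect hidden by carry-over can be computed from a decay half-life.* The documents give no decay rate, and a calculation based only on loss in the sham arm ignores further gain in the active arm.
- *The plan will report a null result as failure.* It has no such rule; it simply does not say how a null result is to be read.

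**Conclusion.** The point holds as a mismatch between objective and design. The Synopsis objective cannot be met by any randomised comparison in the trial. That comparison estimates continued active PEMF versus a switch to sham for at most 60, 46 or 30 days, after 60, 74 or 90 active days, in subjects with a 1-point NPRS decrease. Sham-arm subjects spend 50%, 62% or 75% of the 120 days on active PEMF. These figures come from the protocol's own schedule and need no outside assumption beyond treatment to Day 120 at nominal visit days.

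How much of a true effect the comparison would miss cannot be stated from the documents; the illustration in Step 4 runs from 0% to 100% seen. No sample-size or power figure is affected, because none is claimed. The withdrawal design itself is legitimate. What should change is the claim attached to it.

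**What to change.** 1. Reword the Synopsis objective to say: *compare continued active PEMF with sham for about 30 to 60 days, after 60 to 90 days of open active PEMF, on VPT and QST at Day 121 in subjects with at least a 1-point NPRS decrease.*
2. Bring the closing sentence of Section I into line with the same comparison.
3. Align Section II, which claims effectiveness over 120 days without naming a comparator.
4. Label any change from Day 0 during induction as uncontrolled. If it is reported, tabulate it for all enrolled subjects rather than only those later randomised.
5. Add to Section VI.C that absence of an active-sham difference does not by itself show absence of a PEMF effect, because carry-over from the active lead-in cannot be excluded.

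**Cost.** Items 1, 2, 3 and 5 are protocol wording, carried through to the SAP; the claim becomes narrower. Item 4 needs a small extra tabulation because the efficacy tables now cover randomised subjects only, but VPT and QST are already scheduled at Enrollment and Days 15, 30, 45 and 61 for everyone enrolled. No treatment, visit, assignment or sample size changes.
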